2. SUMMARY AND BACKGROUND

2.1. SUMMARY

We propose to develop and test the implementation of a centralized **Injury Liaison Service (ILS)** to prevent injurious falls in four NH facilities. We will engage stakeholder groups (including NH staff, families, and administrators) and implementation scientists to refine and test the ILS. The ILS will combine successful elements of a Fracture Liaison Service (FLS) and a virtual case based staff education program with the goal of decreasing injurious falls in nursing home residents. ***This service delivers guideline-recommended fall prevention and osteoporosis care consistent with quality improvement initiatives; study activities are limited to data collection to evaluate this program.*** Our central hypothesis is that the ILS model will reduce *injurious falls* by changing care delivery in 2 areas: deprescribing psychoactive and cardiometabolic drugs to reduce falls, and increasing osteoporosis treatment to prevent injury in the setting of a fall.

2.2. Background and Significance

Burden of injurious falls in the NH: The incidence of falls in U.S. NHs is extraordinary: 150 falls/100 bed years.¹ Consequently, falls are the leading cause of hospitalization and ED visits among NH residents.² Five to eleven percent of falls in the NH result in major injury, defined as a fracture, joint dislocation, laceration requiring sutures, or serious hemorrhage.^{1,3} Approximately one-half of injurious falls are fractures.³

Injurious falls are costly: the annual direct cost of managing hip fractures alone in U.S. NH residents exceeds \$665 million.⁴ For a single, average sized NH, the annual direct cost of injurious falls may equal \$284,000.⁵ In addition, injurious falls lead to pain⁶, functional decline,^{7,8} diminished quality of life,⁸ and frequent litigation. CMS has determined that the proportion of NH residents experiencing an injurious fall is an important quality metric,⁹ yet no standardized approach to prevent injury exists.

Efficiently target the intervention: A practical approach to preventing injury in the resource-constrained NH environment requires identification of residents at greatest risk for targeted interventions. Previously, our group published a model that estimates the two-year risk of hip fracture in NH residents: Fracture Risk Assessment in Long term care (FRAiL).¹⁰ This model is derived entirely from data collected for the validated¹¹⁻¹⁶ and routinely collected in all nursing homes through the Minimum Data Set (MDS). The model identified a unique pattern of risk factors for hip fracture not seen in community dwellers: the strongest predictors of fracture were related to falls, rather than bone mineral density (e.g., falls history, wandering). In the derivation sample, the concordance index (C-index) was 0.71 in women and 0.69 in men. We have validated the model to predict the two-year incidence of non-vertebral fracture and hospitalized injurious falls, and model performance is similar (C-index for non-vertebral fracture=0.66; for hospitalized injurious falls=0.65).

Medication management prevents injurious falls: In order to prevent injurious falls it is necessary to 1) remove modifiable risk factors for falls, and 2) manage osteoporosis such that a fracture is less likely to occur in the setting of a fall. Medications are one of the most common and modifiable risk factors for falls and osteoporosis in the NH.

Deprescribing: Strong evidence from clinical trials supports deprescribing (i.e., discontinuing or reducing the dose of) psychoactive^{17,18} and probably cardiometabolic drugs^{19,20} as an effective strategy to prevent injurious falls in NH residents. In one study, seven pairs of NH facilities were randomized to receive individualized assessments from an external, multidisciplinary team.¹⁸ Recommendations included psychoactive deprescribing. The authors achieved 46% adherence with deprescribing recommendations, and a 19.1% reduction in recurrent fallers. The intervention reduced the rate of injurious falls by 31.2%. Among older community dwellers,

reduction of psychoactive drugs resulted in a 39-66% reduction in recurrent falls.^{17,21} Two observational studies have demonstrated a reduction in falls and orthostasis after deprescribing cardiometabolic medications in older adults attending falls clinics, and systematic reviews provide moderate evidence of benefit in a lower risk community population.²² This benefit is likely greater in a NH population, who are at higher risk for hypotension, hypoglycemia, and orthostasis.

Osteoporosis Treatment: Osteoporosis treatment rates are extremely low in NH residents, even among patients at high risk for fracture.²³ This is concerning given evidence to suggest that treatment is probably cost effective in persons with life expectancies as low as 2 years.²⁴ In a large sample of NH residents, we compared the incidence of hip fracture in new bisphosphonate users as compared with new calcitonin users, matched 1:1 with propensity scores (n=10,418). New users of bisphosphonates had a 17% reduced risk of hip fracture (95% CI, 0.71, 0.98) over mean follow-up 2.5 years (*under review*). These findings are consistent with small trials that suggest bisphosphonates may reduce the risk of clinical fracture²⁵ or vertebral fracture²⁶ in NH residents. Further, calcium and vitamin D supplementation has been shown to decrease the risk of non-vertebral fracture by 32% over 18-months in a large RCT of ambulatory NH residents.²⁷

Overcoming implementation barriers: One of the biggest barriers to implementing clinical guidelines in the NH setting is lack of staff knowledge.²⁸ Our team has experience using a case-based video-consultation program designed to provide geriatric expertise in the care of dementia residents to community-based NHs.²⁹ Among the 11 facilities that received the video-consultation program (ECHO-AGE), staff reported improved knowledge of non-pharmacologic strategies to manage behaviors with dementia. Further, facilities receiving ECHO-AGE were less likely to use physical restraints (OR= 0.25, 95% CI 0.06, 1.04) and antipsychotic drug prescriptions (OR= 0.83, 95% CI 0.68–1.02) as compared with residents in the 22 matched facilities with usual care.³⁰ We propose to incorporate a virtual case based staff education program to improve education regarding medication management and falls prevention in residents with Alzheimer's Disease and Related Dementias (ADRD).

Ineffective communication between front-line providers and interdisciplinary staff is another major barrier in implementing individualized, multifactorial injury prevention strategies.²⁸ Successful intervention programs in the NH must change care philosophy,³¹ which requires strong communication among all members of the interdisciplinary NH team. We have previously conducted a number of trials to optimize medication prescribing and prevent falls in the NH setting.³²⁻³⁴ Our proposed model will use a centralized Injury Prevention (IP) Nurse and the virtual case based staff education program to develop an Injury Prevention Plan which reflects staff/resident/family and provider input. The Injury Prevention Plan uses a standard template, but it is individualized to each resident. This template will allow the physician or nurse practitioner to easily review, modify, accept or reject the proposed recommendations. As part of Aim 1, we will interview patients or their proxies, nursing assistants, nurses, and medical providers in order to identify key barriers to communication, and a human factors expert will help work with our team, including implementation scientists, to enhance communication during implementation.

In the current proposal, we will refine and test the implementation of a centralized Injury Liaison Service (ILS) to prevent injurious falls in the NH. Key features of the ILS are depicted in **Figure 1**. The FRAiL model will be used to automate identification of residents at highest risk for injurious falls. The ILS will include a nurse who

Protocol Number: 1.11 Version Date: February 14, 2022 Page

[figure not shown]

Figure 1. Key Components of an Injury Liaison Service designed to prevent injurious falls in Nursing Home Residents

works remotely across multiple facilities with support from a part-time Interdisciplinary Team in order to make medication recommendations to prevent injury. Among high risk residents, the IP nurse will coordinate deprescribing of fall-related medications, osteoporosis management, staff support of behavior management using video case conferencing, and shared decision making with residents and/or families.

2.3. Study Design

This protocol describes refinement and pilot testing activities for the Injury Liaison Service outlined above. The following study designs will be employed:

- 1. Qualitative interviews** will be conducted with approximately 10 NH staff (i.e., nurse, certified nurse aide (CNA), physician, and nurse practitioner who have been employed in a nursing facility for at least 3 months) to gain a better understanding of effective and non-effective injury prevention strategies. Information from these interviews will be used to refine the program during co-design meetings with key stakeholders
- 2. A non-randomized pilot program in four nursing home facilities** will provide data on the implementation of the ILS Program. This includes cross-sectional measures of acceptability, demand, practicality, and feasibility obtained from the electronic medical record (EMR), the IP nurse, and a **post intervention survey** with approximately 60 staff across the four facilities. A **pre-post study design** will be employed in order to measure the safety and efficacy of the ILS Program. Safety and efficacy outcomes will be measured at the resident level.

2.4. Outcome measures. The list of measures, data source, and targets are summarized in Table 1 and described in detail below.

Table 1. Proposed Measures of Implementation, Efficacy, Safety, and Validity with Data Source and Target/Goal

Type	Outcomes	Data Source	Target/Goal
Implementation			
Acceptability	Family acceptance of recommendations	IP Nurse Tracking, staff survey	$\geq 50\%$
	Provider acceptance of recommendations		$\geq 50\%$
	Provider satisfaction		$\geq 80\%$
	Staff participation in virtual case based education program		10 staff/NH/mo.
Demand	Proportion eligible for intervention	IP Nurse Tracking	20%
	Proportion of high risk residents with deprescribing recommendations		50%
	Referral rates to virtual cased based education program		15%
Fidelity	Proportion of targeted staff completing intervention checklists	IP Nurse Tracking	90%
	Cost of IP Nurse per resident		\$225

Practicality	NH staff time	IP Nurse Tracking, staff survey, EMR	<2 hour/mo.	Acceptability: (Primary) Number of families that accepted one or more medication recommendation/ number of families offered a recommendation; Number of patients where
	High-risk Resident 6-mo attrition (death, leave NH)		<40%	
Fidelity/Safety				
Fidelity	No. of deprescribed medications at 3-6 months	EMR	≥1	
	Osteoporosis medication initiation		70%	
Safety	Behaviors	MDS	<10% increase	
	Functional Decline			
	Unscheduled medical visits	EMR	≤2/facility	
Validation				
Outcome Measure	Injurious falls	MDS and Chart Review	>90% sensitive, >95% specific	

the provider accepted one or more recommendations / number of patients with a medication recommendation; % of staff that indicated they were satisfied or very satisfied with the ILS; proportion of staff that attended one or more virtual case based education sessions

(Secondary) number of total medication recommendations accepted/ total number of medication recommendations; proportion of staff that attended two or more virtual cased based education sessions.

Demand: We will use the FRAiL model to identify residents at greatest risk of injurious falls who are eligible for the ILS Program. Residents with an estimated 2-year risk of hip fracture of ≥5%, or similar target, will be considered high risk and eligible for the program. The facility staff will also be able to refer other at risk patients for participation in the program. Other demand outcomes include the proportion of high risk residents with one or more deprescribing recommendations or with a recommendation for osteoporosis treatment, AND referral rates to virtual case based education sessions, defined as the proportion of high risk residents discussed in these sessions.

Fidelity: At each facility, we will identify targeted staff including nurses and medical providers (physicians, nurse practitioners, or physician assistants) who will be asked to complete the program checklists. Our primary measure of fidelity will be the proportion of staff that complete ≥ 75% of requested checklists. As a secondary fidelity measure we will examine the proportion of resident checklists completed by a provider.

Practicality: We will estimate cost by monitoring the amount of time the IP nurse spends on each eligible resident. Other outcomes include the estimated amount of time the staff spend on the ILS service by self-reported survey AND the six-month attrition of eligible residents from the NH facility due to transfer, discharge to community, or death, as determined by the IP nurse from chart review.

Fidelity: Fidelity will be measured as the average number of medications that were deprescribed at 1 and 4 months among high risk residents, as well as the proportion of high risk residents with a prescription for an osteoporosis medication at 1 and 4-months. The IP nurse will review the EMR to determine medications at 1 and 4 months after medication recommendations are finalized.

Safety: Detailed resident-level data collection includes the following potential adverse events related to medication changes: 1) escalating behaviors, worsening depression, or functional decline following psychoactive deprescribing; 2) unplanned medical visits for hypertension,

tachycardia, or hyperglycemia for cardiometabolic deprescribing; 3) new gastroesophageal reflux disease or esophagitis following bisphosphonate prescription.

Each facility will provide two Minimum Data Set (MDS) assessments following baseline in order to characterize the occurrence of these adverse events. Behaviors and depression will be measured using validated scales from the MDS.^{35,36} Any worsening of behavior (any category) as assessed by nursing will be considered. Worsening depression will be defined as a 1-point increase in the PHQ-9 or PHQ-9-OV. This corresponds with meaningful change in depression severity.³⁷ Any increase in the frequency of reported verbal, physical, or other behaviors will be considered. Functional decline will be defined as a 3-point increase in the MDS Activities of Daily Living Scale. A 3-point increase corresponds with complete loss of a single ADL or incremental loss of 2 ADLs.^{38,39} Change in depression, behaviors, and functional status will be measured using the MDS assessment closest to and preceding implementation and the subsequent MDS assessment.

Lastly The IP nurse will enter all targeted adverse events into the RedCap database. At the next study team meeting, or within 14 days, the IP nurse will review the event with the team for a determination of an adverse event using the validated Drug Withdrawal Probability Scale^{40,41} to determine if there is a probable, possible, or doubtful relationship between the medication change and the adverse event. Discordance will be adjudicated by a third investigator (physician).

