10. STATISTICAL CONSIDERATION

This is a pilot study to test design and test implementation of the ILS Program in four nursing home facilities. We will largely use descriptive statistics to present our results, and to inform the sample size calculation for a future pragmatic RCT. The following statistical considerations will be considered:

- Qualitative Study (Aim 1) - Using NVivo software, investigators will identify themes and touch points described by participants in an open coding process. Short audio clips may be created to illustrate each theme and re-organized into *ethnography of the fall prevention experience*, with audio clips preserving the family and staff voices.⁴² A similar process will occur to analyze the post-implementation interviews from staff and proxies, in order to identify themes surrounding implementation barriers.

In addition, the team will use process *flow mapping* techniques to describe each step, however minor, necessary to 1) program the automatic calculation of injury risk using the FRAiL model, 2) deprescribe psychoactive and cardiometabolic medications associated with falls and injury, 3) prescribe osteoporosis treatment to reduce injury risk in the setting of a fall, and 4) introduce other best practices to prevent injurious falls in the NH.

- ILS Implementation (Aim 2) - Quantitative measures of acceptability, demand, fidelity, and practicality as defined in **Table 1** will be described using descriptive statistics. As is standard in pilot studies, our sample size target is based on the expected proportion of high-risk residents in the 4 pilot facilities and no statistical testing is planned, thus, formal power calculation was not conducted. However, our goal is to achieve 50% adherence with suggested medication changes, and our sample of 80 residents is sufficient to demonstrate this with a 95% Confidence Interval of +/- 5% [95% CI assuming SD 10% is 47.8-52.2%; assuming SD 20% is 45.6-54.5%]. We will refine the ILS Program until >50% acceptance of ILS recommendations is achieved, using the targets set in Table 1.

Following current recommendations, we will not power the future pragmatic trial on the results of this small implementation study with unstable efficacy estimates, but rather we will use our clinical knowledge and results of previously published trials of deprescribing in order to inform the sample size calculation.⁴³

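### The 50% acceptance target sits on a measure that counts any one accepted recommendation, while Section 10 describes 50% adherence and gives a precision that fits a different quantity

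*Combined protocol and SAP*

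**What the plan says.** Section 2.4 has two primary acceptance measures. For families: "Number of families that accepted one or more medication recommendation/ number of families offered a recommendation". For providers, it is the number of patients where "the provider accepted one or more recommendations / number of patients with a medication recommendation". Table 1 sets a target of at least 50% for family acceptance and at least 50% for the row "Provider acceptance of recommendations".

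Section 2.4 also lists, as a secondary measure, "number of total medication recommendations accepted/ total number of medication recommendations". No target is attached to it, and it does not say whether acceptance by the family or by the provider is counted.

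Section 10 says that "our goal is to achieve 50% adherence with suggested medication changes", and that "our sample of 80 residents is sufficient to demonstrate this with a 95% Confidence Interval of +/- 5" percent. The supporting bracket reads "95% CI assuming SD 10% is 47.8-52.2%; assuming SD 20% is 45.6-54.5" percent. It continues: "We will refine the ILS Program until >50% acceptance of ILS recommendations is achieved", and refers back to the Table 1 targets for that rule.

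**The concern.** The target and the stated goal share the figure 50% but refer to different quantities. A measure that counts a resident as accepting once any one item is accepted depends on how many items were offered as well as on willingness to accept them. Adding recommendations raises it even if willingness stays the same. Adherence with suggested changes, in the ordinary sense, does not behave that way.

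Two things follow. The refinement rule in Section 10 is judged on the Table 1 targets, so refinement could stop while most recommended changes are being refused. And the ±5-point precision offered to justify 80 residents does not apply to the measure that carries the target.

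**Working it through.** **Inputs from the documents.** n = 80, goal 50%, SD 10% or 20% (Section 10); the one-or-more definition (Section 2.4); targets of at least 50% (Table 1). **Not in the documents:** the number of recommendations per resident, k, and the correlation of acceptances within a resident, ρ. Values for these are assumptions.

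**Step 1. Reproduce the plan's interval.** For a mean of per-resident percentages, the 95% half-width is 1.96 × SD / √80, with √80 = 8.944.

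- SD 10%: 1.96 × 10 / 8.944 = 2.2, giving 47.8–52.2%.
- SD 20%: 1.96 × 20 / 8.944 = 4.4, giving 45.6–54.4%. With the t distribution on 79 degrees of freedom it is 45.5–54.5%.

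Both agree with Section 10 to within 0.1 point. The calculation therefore treats adherence as a continuous percentage per resident.

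**Step 2. The same calculation for the primary measure.** A yes/no indicator with proportion 0.5 has SD √(0.5 × 0.5) = 50%. The half-width is 1.96 × 50 / 8.944 = 11.0 points, giving 39.0–61.0%. This uses all 80 residents. The denominators in Section 2.4 are residents with a recommendation and families offered one, so they can only be 80 or fewer of the planned sample. No assumption about k or ρ is needed.

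**Step 3. Direction of the mismatch.** For each resident, the one-or-more indicator (0 or 100%) is at least as large as the percentage of that resident's recommendations accepted. It is strictly larger whenever acceptance is partial. The one-or-more proportion therefore cannot fall below the mean per-resident percentage, and the two are equal only if every resident is all-or-none.

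**Step 4. How far apart, by assumption.** With per-recommendation acceptance p, independence and the same k for everyone, P(any) = 1 − (1 − p)^k. Setting this to 0.5 gives p = 1 − 0.5^(1/k). With correlation ρ (beta-binomial), P(none) is the product over j = 0 to k − 1 of [(1 − p)(1 − ρ) + jρ] / [(1 − ρ) + jρ], set to 0.5 and solved for p.

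| Value of p at which the one-or-more measure reaches 50% | k = 1 | k = 2 | k = 3 | k = 4 |
|---|---|---|---|---|
| ρ = 0 | 50.0% | 29.3% | 20.6% | 15.9% |
| ρ = 0.3 | 50.0% | 34.2% | 27.4% | 23.6% |
| ρ = 0.5 | 50.0% | 38.2% | 32.8% | 29.6% |
| ρ = 0.8 | 50.0% | 45.0% | 42.6% | 41.1% |

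With mixed counts and independence:

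- Half with one and half with two: 0.5p + 0.5[1 − (1 − p)²] = 0.5 reduces to p² − 3p + 1 = 0, so p = 38.2%.
- 30% with one, 40% with two, 30% with three: p = 30.7%.
- 50% with one, 30% with two, 20% with three: p = 35.6%.

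Conversely, if p really were 50% with independence, the one-or-more measure would read 75%, 87.5% and 93.8% for k = 2, 3 and 4.

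**The case against.** The best defence is that this is a descriptive pilot. No testing is planned, the later trial will not be powered on these results, and reporting acceptability per family or per resident is a legitimate choice. The per-recommendation proportion is already planned as a secondary measure, so the information will exist. All of that stands, and it limits the stakes. It does not make Sections 2.4 and 10 describe the same quantity.

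Three stronger readings are tempting, and the documents do not support them.

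- **That the 50% target amounts to 16–29% acceptance.** This needs two to four recommendations for every resident and independent decisions. Table 1 expects only half of high-risk residents to have a deprescribing recommendation, so some may have a single item. One provider co-signs one plan per resident, which makes positive correlation likely. Both push the threshold back towards 50%.
- **That calcium and vitamin D alone could carry the program with no deprescribing.** Most enrolled residents may meet the Appendix 1 criteria for these supplements. The documents do not say how many already take them, or whether a supplement counts as a medication recommendation. Table 1 also has separate fidelity targets: at least one deprescribed medication, and 70% osteoporosis initiation. An absence of deprescribing would fail the first. Those targets would expose the problem, but they do not repair the acceptance criterion or its precision.
- **That swapping the primary and secondary labels is enough.** The secondary measure is a pooled ratio that gives more weight to residents with many recommendations, whereas Section 10's SDs imply a mean of per-resident percentages. The pooled ratio also leaves open whose acceptance it counts.

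**Conclusion.** The inconsistency is real. The measures carrying the 50% targets are not the adherence that Section 10 sets as its goal and sizes, and the refinement rule rests on those targets. Whenever some residents receive two or more recommendations and acceptance is not perfectly correlated within a resident, the targets can be met with per-recommendation acceptance below 50%. How far below cannot be fixed from the documents: the scenarios worked here run from 16% to 45%, depending on the assumed counts and correlation.

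The precision mismatch rests on less. For a yes/no measure near 50% with 80 residents the half-width is about ±11 points, against the stated ±5. This is worth correcting before results are reported, but it does not undermine the pilot as a whole.

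**What to change.** In Section 2.4, Table 1 and Section 10, attach the 50% goal and the refinement rule to one per-recommendation adherence measure, defined separately for families and providers. Either of these would serve:

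- the mean per-resident percentage of recommendations accepted, which is the quantity that Section 10's SDs describe; or
- accepted over total recommendations, with a confidence interval that allows for clustering within resident.

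Report it by recommendation type (deprescribing, antiresorptives, calcium and vitamin D), together with the distribution of the number of recommendations per resident. Keep the one-or-more measure as descriptive.

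If the one-or-more measure keeps the target, restate its precision as about ±11 points and stop describing it as 50% adherence.

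No new data are needed: individual recommendations and their acceptance must already be recorded for the secondary measure. The cost is a short amendment with explicit definitions, and reported acceptance that will look less favourable.

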2.6. Sample Size and Population

We anticipate enrolling approximately 10 NH staff and 10 patient/families for an interview on injury prevention.

We anticipate approximately 20% of long-stay residents at the 4 facilities will be eligible for the medication management program (n=80). See **Section 10, Statistical Considerations** for a full explanation of sample size.

We anticipate conducting interviews to assess the acceptability and practicality of the ILS Program on 60 staff members across the four facilities.

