6. STUDY ACTIVITIES

The qualitative Aim 1 study will be conducted in the 2 facilities in North Carolina.

All four NH facilities (2 in Boston area, 2 in Durham, NC area) will receive the same ILS Quality Improvement Program. Each facility will participate for a total of 18 months, including a 6-month start-up/planning period, a 6 month implementation period, and a 6 month data collection period. Residents eligible for the ILS Program will be identified during the 6-month implementation period, and each

resident will be followed for up to 6 months.

The ILS Program is consistent with a quality improvement program because it is delivering guideline-recommend

ed fall prevention and osteoporosis care. Study interventions are therefore limited to the data collection procedures described previously to determine the feasibility and acceptability of the ILS program.

However, the

Table 2. Intervention model components, who is responsible, timing and time involved.	
Activity	Who, When, Time Required
High Risk Resident Identification	
FRAiL tool identifies high risk residents from MDS; facility champion may also suggest residents for participation	IP Nurse, monthly, 30 minutes
Resident Data Gathering	
EMR review and relevant data extraction into Redcap database	IP Nurse, 20 minutes/resident
Medication algorithm identifies those potentially eligible for deprescribing and osteoporosis treatment	Automated, database
Injury Prevention Plan Development and Documentation	
Documentation of IPP using standard template	IP Nurse with IDT review during weekly meeting, 5 min/resident
Telephone visit with resident/family for modification/acceptance	IP Nurse 10 min/patient
Telephone visit with Charge Nurse, scheduling of virtual cased based education session if staff has concerns about behaviors	IP Nurse 5 min/patient
Virtual case based education sessions for selected Residents with active behavioral issues	NH LPN, NA, RNs, ILS Nurse, IDT, Family; 15 min/resident; monthly
IPP Implementation and Follow-Up	
IPP placed in medical record for medical team cosignature	IP Nurse, 5 min/patient
Issues/problems discussed during next virtual case based education sessions session	MDS nurse, charge nurse, CNAs, Virtual case based education sessions IDT
1 and 4 EMR review and IPP update	IP Nurse with discussion by IDT as needed, 15 min/patient

components of the quality improvement program are summarized in **Table 2** and described in more details in the following sections.

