7.3 Resident assessments

Resident data will be collected by the IP nurse. Charts are abstracted at baseline and again at 1 and 4 months after the study recommendations are finalized, to determine if medication recommendations were followed, and if there was any evidence of adverse events. The IP nurse will hold weekly brief telephonic huddles (~10-15 minutes) with direct care staff to determine staff perceptions of the program and to collect critical information on data missing from chart, such as behaviors.

Demographic: (baseline; chart and MDS) age, gender, race, ethnicity, length of NH stay and proxy contact information (for mailing study information and ability to opt out) and relationship to resident.

Medical co-morbidity: (baseline; chart review) All active medical diagnoses.

Medications: (baseline, 1 and 4 months; chart review) All prescribed medications and doses.

Functional status: (baseline, 1-6 months follow-up via MDS) We will categorize functional status using the Katz ADLs at baseline and during followup

Falls, fractures, injurious falls: (baseline, 1 and 4 months; also via MDS and falls log) We will ascertain falls and falls with injury from the 2 MDS assessments during followup, the facility falls log, and also from chart review.

Adverse events – other major acute illnesses: (baseline, 1 and 4 months; MDS and chart review) We will consider the following adverse events due to medication changes: 1) escalating behaviors, worsening depression, or functional decline following psychoactive deprescribing; 2) unplanned medical visits for hypertension, tachycardia, or hyperglycemia for cardiometabolic deprescribing; 3) new gastroesophageal reflux disease or esophagitis following bisphosphonate

prescription. Each facility will provide limited MDS data at baseline and during follow-up in order to characterize the occurrence of these adverse events. Change in depression, behaviors, and functional status will be measured using the MDS assessment closest to and preceding the program implementation and the subsequent MDS assessment.

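### The measured IP nurse cost per resident, to be compared with the $225 target, will be understated because it counts only time on individual eligible residents and leaves out the nurse's facility-level time

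*Combined protocol and SAP*

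**What the plan says.** Table 1 (Section 2.4) lists the outcome as "Cost of IP Nurse per resident", with $225 in the target column and no derivation. The Practicality paragraph of the same section gives the only measurement rule: "We will estimate cost by monitoring the amount of time the IP nurse spends on each eligible resident".

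Elsewhere the protocol gives the nurse tasks of two kinds.

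- **Resident-specific (Section 6, Table 2):** chart review and extraction ("IP Nurse, 20 minutes/resident"), the prevention plan ("IP Nurse with IDT review during weekly meeting, 5 min/resident"), the resident or family call ("IP Nurse 10 min/patient"), the charge nurse call (5 min), placing the plan in the record (5 min), and the month 1 and month 4 review (15 min).
- **Not tied to one resident:**
  - High-risk identification is entered in Table 2 as "IP Nurse, monthly, 30 minutes".
  - Section 7.3 adds: "The IP nurse will hold weekly brief telephonic huddles (~10-15 minutes) with direct care staff". Section 8.2 also lists the huddles among the measures that limit withdrawal risk.
  - Section 6.2 has the nurse go through monthly provider feedback with the site champion (no minutes given).
  - Sections 2.5 and 6.2 allow general teaching in the education sessions, beyond the discussion of individual cases.

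**The concern.** The label promises the cost of the nurse per resident, but the rule delivers only the cost of the nurse's time on individual residents. Shared nurse time has no route into the figure, so the error runs in one direction only: the measured cost is too low and the comparison with $225 is too easy to pass.

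The omitted part also behaves differently from the part that is kept. Screening and huddles are largely fixed per facility, so their cost per resident rises when few residents are eligible. A measure that ignores them cannot show how cost depends on caseload, which matters for a service built on one remote nurse covering several facilities. Time not logged during the pilot is hard to reconstruct afterwards.

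**Working it through.** **The plan's own figure.** $225 cannot be reproduced, because no hourly rate, hours budget or list of covered activities is given.

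**Resident-specific time (Table 2).** 20 + 5 + 10 + 5 + 5 + (2 × 15) = 75 min. This assumes 15 min at each of the two reviews; counted once, the sum is 60 min. A 15-min case session for the 15% of residents in the Table 1 referral target would add 0.15 × 15 = 2.25 min.

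**Facility-level time.** The inputs are screening at 30 min monthly, huddles at 10-15 min weekly, a 6-month implementation period (26 weeks), four facilities and 80 residents (Section 2.6). The documents do not say whether screening and huddles are run per facility, or for how many weeks the huddles continue, so these are varied.

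Added time per resident = (screening minutes + huddle minutes) / 80. Share omitted = added / (75 + added).

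| Reading | Screening | Huddles | Added per resident | Share omitted |
|---|---|---|---|---|
| Each facility, 6 months of both | 4×6×30 = 720 | 4×26×(10 to 15) = 1,040 to 1,560 | 22.0 to 28.5 min | 23-28% |
| Once for all facilities, 6 months of both | 6×30 = 180 | 26×(10 to 15) = 260 to 390 | 5.5 to 7.1 min | 7-9% |
| Each facility, huddles 52 weeks | 720 | 4×52×(10 to 15) = 2,080 to 3,120 | 35 to 48 min | 32-39% |
| Each facility, 12 months of both | 4×12×30 = 1,440 | 2,080 to 3,120 | 44 to 57 min | 37-43% |

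In the first row total time is 97.0 to 103.5 min against 75, so cost rises by 29-38% at any hourly rate (22/75 and 28.5/75). On the 60-min base, that row's omitted share becomes 22/82 = 27% to 28.5/88.5 = 32%. Feedback review and general teaching would come on top, but no minutes are given for them.

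**If huddles were treated wholly as research.** Screening alone adds 720/80 = 9 min (9/84 = 11% omitted) or 180/80 = 2.25 min (2.25/77.25 = 3%).

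**Caseload.** Over 6 months the per-facility total is 440 to 570 min (180 + 260 or 390). At 20 eligible residents that is 22 to 28.5 min each. At an assumed 10 it is 44 to 57 min each, while the planned measure would still show about 75.

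**Against $225.** The target is reached at 225/(75/60) = $180/h on resident-specific time, and at 225/(97/60) = $139/h to 225/(103.5/60) = $130/h once screening and huddles are included. At an assumed $40-100/h, 75 min costs $50-125 and 97.0 to 103.5 min costs about $65-173. The largest addition in the table (132 min in all) costs $220 at $100/h.

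**The case against.** The strongest reply is that direct nurse time per resident is a legitimate descriptive measure in a small pilot, and that allocating overhead is a different costing perspective. Section 2.4 does not say other nurse time goes unrecorded, and Table 1 names nurse tracking as a data source. This would settle the matter if the outcome were labelled as direct time. It is labelled as the cost of the nurse, and the stated rule does not deliver that.

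Several narrower objections stand and limit the point:

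- **Case sessions** are partly attributed to residents already: Table 2 budgets 15 min per resident with the nurse present. Only the general teaching is unattributed.
- **Huddles** partly collect study data (staff perceptions, information missing from the chart), so their share of service cost is open. They supply most of the added minutes, for example 260 of 440.
- **Per-facility running** is an assumption. One nurse covers several facilities remotely, and the smaller 7-9% reading cannot be excluded.

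A reader might also infer that the $225 is itself too low, that the pilot would wrongly declare its cost target met, or that a biased cost will carry into the later trial. The documents support none of these. The $225 is a target of unstated origin, not an estimate built from per-resident time. In the central reading, the result against it changes only at rates of roughly $130-180/h, and the documents give no rate. Section 10 treats the Aim 2 measures as descriptive, and no section makes cost an input to the later trial.

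**Conclusion.** The point holds as a one-directional bias in the measured cost. If the costing rule is followed as written, the figure set against $225 leaves out nurse time that the protocol itself schedules. Counting only screening and huddles, the central estimate is that 23-28% of nurse time is omitted. This rests on 75 min of resident-specific time, 80 residents, both activities run in each of four facilities for 6 months, and all huddle time counted as service. Keeping the 75-min base and full huddle time, the readings run from about 7% to about 43%; treating huddles as pure research lowers the bottom of that range to about 3%. The direction is the same in all of them.

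No change in the result against $225 has been shown, and none can be without an hourly rate. This is a cheap improvement, not a threat to the pilot's conclusions.

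**What to change.** - Have the IP nurse log all program time by activity and facility, with service delivery marked separately from research data collection. The huddles need this split most.
- In Section 2.4, define cost per resident as total service-delivery nurse time × a stated hourly rate / number of eligible residents, and compare that figure with $225.
- Report the resident-specific part beside it, so that fixed and per-resident costs can be told apart at other caseloads.
- State which activities the $225 target is meant to cover and how it was obtained.

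The cost is a few extra log entries, one revised definition, and a less favourable cost figure.
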